The STRW intervention consists of 14 weekly concurrent adolescent and parent group sessions. The DLS to be targeted in the intervention include: *Morning Routine* (i.e., completing a morning personal hygiene routine); Laundry (i.e., sorting clothing, using a washing machine and dryer, and folding and putting clothes away); Kitchen/Cooking (i.e., cooking items in the microwave, oven, and stove, safe kitchen practices, cleaning up the kitchen after cooking, and grocery shopping); Self-Management (i.e., managing worry and stress related to learning DLS and transitioning to adulthood); and *Money* Management (i.e., using money to purchase items, evaluating the quality and price of items, understanding and using a checking and savings account, and budgeting money to cover expenses). The above targeted skills are based on the preliminary studies conducted by [name] on common DLS deficits in high functioning adolescents with ASD(Duncan, Ruble, Meinzen-Derr, Thomas, & Stark, in press; Duncan et al., 2014). Several evidence-based strategies will be utilized to help adolescents acquire specific DLS in session and then generalize these skills to the home and the community. Specifically, in adolescent group sessions, visual strategies such as creating a task analysis and checklist of steps (e.g., the steps involved in doing laundry) are used to increase skill acquisition. Technology such as video modeling (e.g., creating a movie of one completing their personal hygiene routine that can be watched on their computer or phone) or apps for smart phones (e.g., money management app, grocery store app, cooking app with videos of recipes) are also used because these have been shown to be an effective way to understand and learn targeted skills in other areas of functioning and increase motivation for learning new skills(Burton, Anderson, Prater, & Dyches, 2013; Satriale, Chance, & Nepo, 2009) in individuals with ASD. Parent participants will receive instruction on how to utilize evidence-based strategies to teach and generalize DLS for adolescents with ASD including a behavior contract, task analysis, chaining, modeling, reinforcement, rewarding reasonable attempts, prompting, prompt fading, generalization, incorporating special interests, visual strategies, self-management, video modeling, and technology(Hume et al., 2014;

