National Autism Center, 2009; Wong et al., 2015). Due to COVID-19, an undetermined number of sessions will be conducted via telehealth using a HIPAA compliant version of Zoom.

STRW In-Person Sessions: The STRW parent sessions will be facilitated by the PI. The STRW adolescent sessions will be facilitated by a psychology post-doctoral fellow and graduate student trainees (e.g., in the fields of psychology and occupational therapy) recruited from the Leadership Education in Neurodevelopmental Disabilities (LEND) training program at CCHMC (see letter of support for additional information).

Group Sessions. Each group session lasts 90 minutes and consists of four main components: (1) Overview of session activities; (2) Updates from group members on progress towards DLS goals being targeted and weekly homework assignments; (3) Divide into separate parent and adolescent groups to work on session-specific content; and (4) Reconvene as a group to summarize and share the activities that were done during the session and discuss homework assignments targeting the DLS goals for the week. Weekly homework assignments will be given to the adolescent to encourage acquisition, maintenance, and generalization of skills to the home and/or community (e.g., do laundry at home, purchase items at a grocery store using a pre-defined budget). Completion of homework assignments will be tracked at each session via parent and adolescent report. In addition, parents will be contacted by email or text message (parent preference) each day to track completion of homework assignments. Throughout each session, the therapists will facilitate the development of a behavior contract that specifies when the newly taught DLS will be practiced and the contingent reward that the parent will provide (see Figure 3 for an example of a completed behavior contract). At the end of each session, parent and adolescent pairs will complete feasibility, acceptability, and satisfaction surveys.

Adolescent Group Sessions.

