decreased motivation from teen to work on DLS, developing parental skills to foster independence with DLS, identifying rewards to increase the likelihood of continued skill development) and assist in problem-solving these barriers.

STRW Telehealth Sessions: The STRW parent sessions will be facilitated via video, using the HIPAA compliant version of Zoom. The format will be similar to the in-person sessions.

The STRW teen sessions will be scheduled and run by a psychology post-doctoral fellow or graduate student trainee. The sessions will be scheduled for 1 hour, and both parent and teen will participate. Targeted daily living skills will be practiced using the participant's home appliances and materials.

The PI will provide weekly supervision to all fellows and trainees that facilitate the STRW adolescent sessions. Both in-person and telehealth sessions will be videotaped and coded for treatment adherence and fidelity. A blinded coder will complete a treatment adherence and fidelity checklist on 25% of the sessions chosen at random.

PEERS Control Group:

Due to COVID-19, an undetermined number of sessions will be conducted via telehealth using a HIPAA approved version of Zoom.

PEERS In-Person Sessions: PEERS is the control group and consists of 14 weekly (90 minute) concurrent sessions that both adolescents with ASD and their parents attend. Social-communication and interaction skills such as building friendships, handling arguments, dealing with teasing, arranging and attending outings with peers are targeted through direct instruction, modeling, and practice in adolescent sessions. Parents are taught how to build and reinforce social skills outside of sessions. The purpose of the control group is to allow us to assess change in daily living skills in a group of high functioning adolescents with ASD who have deficient daily living skills but do not receive systematic behavioral treatment targeting specific skills using evidence based strategies.

PEERS Telehealth Sessions: The PEERS parent and teen sessions will be run simultaneously using the HIPAA compliant version of Zoom. This will require families to have two devices so both parent and teen can attend sessions at the same time.

DURATION:

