A possible indirect benefit of this research is the knowledge that results from this project might positively impact the ability of researchers to obtain a better understanding of issues related to the postsecondary education, employment, and the overall transition to adulthood for individuals with DD. Further, this may lead to an increase in better services and supports as they make the transition to adulthood.

POTENTIAL RISKS, DISCOMFORTS, INCONVENIENCES AND PRECAUTIONS:

The risks associated with participating in the study are considered to be minimal and are commensurate with everyday risks. All of the measures used in this study have been used in previous research. Participants may experience transient emotional distress upon completing some of the interviews and questionnaires, which ask about their child's development or affective state. The clinicians and researchers who will be conducting the assessments are trained to assess and minimize any discomfort that results from the interviews or questionnaires. In the event that a participant finds the psychological evaluation mildly anxiety provoking, interviewers will express empathy and test-appropriate encouragement and reassurance. All participants will be informed that their participation is completely voluntary, and that they are free to withdraw from the study at any time.

The population of the study does include women capable of bearing children; however the study poses no additional risk to pregnant women.

RISK/BENEFIT ANALYSIS:

Based on the stated potential benefits and potential risk, we believe the study is considered "Minimal Risk", without potential direct benefit to the participants. Based on this assessment, we believe there is no need for a Data Safety Monitoring Board. The P.I. will be responsible for monitoring the study data through consistent communication with the coordinator during each phase. We will report any unanticipated problems and unexpected adverse events per CCHMC policy R-18.

PRIVACY & CONFIDENTIALITY:

Participants who indicate that they no longer wish to participate will not be contacted again for any reason.

Participants will be informed that all information they provide will be kept confidential unless there is a risk of harm to the participant or others (e.g., abuse, suicide, homicide), and/or if a clinician is required by law to make a report. Appropriate referrals will be provided in situations where follow-up clinical services are required.

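### Neither arm has a planned way to ask about, record or tabulate harms, although STRW alone adds stove, oven and home-appliance practice

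*Combined protocol and SAP*

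**What the plan says.** **Risk.** The section on potential risks opens with a statement about the study as a whole: "The risks associated with participating in the study are considered to be minimal and are commensurate with everyday risks". It then becomes specific twice, both times about assessment. The first is "Participants may experience transient emotional distress upon completing some of the interviews and questionnaires"; the second begins "In the event that a participant finds the psychological evaluation mildly anxiety provoking". A line on pregnancy follows. No intervention activity is named.

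**Oversight and reporting.** The Risk/Benefit Analysis section classes the study as Minimal Risk on the basis of the stated benefits and risks, and adds "we believe there is no need for a Data Safety Monitoring Board". The principal investigator monitors study data through regular contact with the coordinator. The event rule is a single sentence: "We will report any unanticipated problems and unexpected adverse events per CCHMC policy R-18".

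**What STRW participants do.** The STRW Intervention Group section lists "cooking items in the microwave, oven, and stove, safe kitchen practices" among the targeted skills. Under Adolescent Group Sessions, each adolescent cooks one or two items with therapist instruction and feedback. Under STRW Telehealth Sessions, skills are practised with the participant's "home appliances and materials", with the parent taking part. Weekly homework is done at home or in the community. The Facilities section assigns the Metabolic kitchen to the STRW group.

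**What PEERS participants do.** The PEERS Control Group section describes social-skills teaching and practice. It mentions no cooking or appliance work.

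**Contact between sessions.** For STRW, under Group Sessions, "parents will be contacted by email or text message (parent preference) each day to track completion of homework assignments". Parent and adolescent pairs also fill in short surveys after each STRW session. Neither is described for PEERS.

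**The concern.** The arm that adds physical activity is the one whose activities the risk section does not discuss. Participants are selected for deficient daily living skills, and the curriculum's own safety teaching shows that kitchen hazard was foreseen. The plan nevertheless describes no way of finding out whether anyone was hurt, beyond what staff happen to see or families happen to mention.

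What is at stake is how the trial's safety can be described afterwards. If nobody is asked, a report of no events cannot be told apart from a failure to look. If a few events do surface unprompted, a comparison between arms is doubtful, because STRW families have more occasions to mention something.

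**Working it through.** There is no safety figure in the documents to reproduce: no event rate, safety sample size or harm endpoint. The check is mainly a search of the text, followed by arithmetic for scale.

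**Step 1: is a harm item described anywhere?**

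| Place in the protocol | What is collected | Injury or adverse-event item? |
|---|---|---|
| Baseline Pre-Assessment; Post-Treatment and 6-Month Follow-up | Questionnaires, parent interview, medication, services and therapies | None described |
| Measures | Adaptive behavior, executive function, social skills, behavior and emotion ratings, parenting, family and community scales | None described |
| 12-, 18- and 24-month calls; outcomes survey | Vineland-3 at the calls; current status of the young adult | None described |
| STRW sessions | Homework tracking, daily message, end-of-session surveys, video coded for fidelity | None described |
| PEERS sessions | Session content only | None described |
| Analyses; Missing data methods | Efficacy and exploratory analyses | No harm table by arm |

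The BASC-3, given in both arms, rates behavior and emotions, so general distress may show up as a score. It is not presented as a record of harmful events.

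**Step 2: does the reporting rule fill the gap?** It cannot be relied on to do so. The rule turns on whether an event is unanticipated or unexpected. The protocol defines neither term and does not reproduce policy R-18. A burn is not among the listed risks, so it might count as unexpected and be reported. Safe kitchen practice is taught, so it might instead count as expected. The text does not settle which. In either case, a rule for passing events on does not create a way of detecting them.

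**Step 3: what would a zero count mean?** Input: 35 participants in STRW (Study Design).

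- With everyone asked and no events, the exact one-sided 95% upper limit is 1 − 0.05^(1/35) = 0.082, or 8.2%.
- If only a fraction c of injured participants ever came to notice, the same zero would bound c × risk at 8.2%, so the limit on the true risk would be 8.2%/c. For assumed values c = 0.9 and c = 0.3 this gives 0.082/0.9 = 9.1% and 0.082/0.3 = 27%. Under the plan as written c is unknown, so no limit can be stated.

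**Step 4: could there be anything to find?** The true injury risk p is an assumption. The chance of at least one injured participant among 35 is 1 − (1 − p)^35.

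| Assumed p | Chance of at least one in 35 |
|---|---|
| 1% | 30% |
| 2% | 51% |
| 5% | 83% |
| 10% | 97% |

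Even at low assumed risks, an event in this arm would be no surprise.

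**The case against.** The strongest reply is that the hazard is ordinary and supervised. Cooking and laundry are household tasks, and the general sentence about everyday risks plausibly covers them. Therapists instruct while adolescents cook, parents join telehealth teen sessions, sessions are videotaped, and staff would see an injury that happened in front of them. This stands as far as it goes. It limits the gap mainly to unsupervised homework and to the lack of a systematic record. It does not supply that record.

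It is also fair to say that the plan promises no safety comparison between arms, and that a trial this small could establish little about rare harms even with full questioning. The 8.2% limit shows as much. That is a reason to keep the remedy small.

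A reader might infer three stronger things that the documents do not support:

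- **That a kitchen burn is excluded from reporting.** The policy is not reproduced, and an injury missing from the risk list could well be classed as unexpected.
- **That the Minimal Risk label or the decision against a monitoring board is wrong.** Nothing in the documents shows that naming the kitchen activities would change either.
- **That the difference in contact gives a measurable reporting bias.** A homework message is not equivalent to a 90-minute session. The messages do not ask about injuries, both arms share the assessment visits, and the missing-data section promises close contact with families without limiting it to one arm. The likely direction of unevenness is towards STRW; its size cannot be derived.

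The consent pages and a small part of the document were not available, so participant-facing risk wording was not checked.

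**Conclusion.** The point holds as a gap in harm ascertainment. Followed exactly, the plan yields no systematic harm data in either arm and none that can be compared, while STRW alone adds stove, oven and home-appliance practice. An absence of reported events could not be taken as evidence of safety.

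The size of any missed harm is unknown; the injury risks and detection fractions used above are assumptions for scale only. The conclusion rests on the absence of a described harm item and table in the available text, not on any reading of policy R-18. Primary efficacy results are not affected. This is a low-cost improvement rather than a flaw in the trial's main inference.

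**What to change.** 1. In both arms, ask the same brief, fixed question on injury or distress at contacts that already exist: at least the post-treatment and 6-month assessments, and weekly sessions where practical.
2. Record every event, whether or not it was expected, and add a table by arm to the analysis plan.
3. Name the kitchen and appliance activities in the risk section. This wording change alone would not close the gap.
4. The document is dated November 2022 and the study was due to run through December 2022. If sessions are already complete, state in the report that harms were not systematically collected, and do not present an absence of reports as a safety finding.

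The cost is one short question, one REDCap field, one table, a little data entry and some trivial events recorded. No new visits are needed.
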